#### **11.1.2 Disease Parameters**

Measurable Disease Measurable lesions are defined as brain lesions that can be accurately measured in at least one dimension) as  $\geq 10$  mm by Gd-MRI. All tumor measurements must be recorded in millimeters.

Note: Tumor lesions that are previously treated with stereotactic radiosurgery are not allowed as target lesion.

Non-measurable disease All other lesions including small lesions (longest diameter  $< 10$  mm are considered non-measurable disease.

Note: Cystic lesions that meet the criteria for radiographically defined simple cysts should not be considered as malignant lesions (neither measurable nor non-measurable) since they are, by definition, simple cysts.

‘Cystic lesions’ thought to represent cystic metastases can be considered as measurable lesions if they meet the definition of measurability described above. However, if non-cystic lesions are present in the same patient, these are preferred for selection as target lesions.

Target lesions: All measurable brain metastases  $\geq 10$  mm should be identified as target lesions and recorded and measured at baseline. Target lesions should be selected on the basis of their size (lesions with the longest diameter but in addition should be those that lend themselves to reproducible repeated measurements. It may be the case that, on occasion, the largest lesion does not lend itself to reproducible measurement in which circumstance, the next largest lesion which can be measured reproducible should be selected. A sum of the diameters for all target lesions will be calculated and reported as the baseline sum diameters.

Non-target lesions: All other lesions should be identified as non-target lesions and should also be recorded at baseline. Measurements of these lesions are not required, but the presence, absence, or in rare cases unequivocal progression of each should be noted throughout follow-up.

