##### **Definition of CNS response to eribulin mesylate**

Residual enhancing, non-enhancing, or minimally enhancing tumor:

PR or CR should be confirmed at least 4 weeks after scan showing response.

**Complete Response (CR):** shall be defined as the circumstance when the tumor is no longer seen by neuroimaging, with the patient off all steroids, or on adrenal maintenance only; CR will be coded only if confirmed by a second CT/MR scan performed a minimum of 4 weeks after the initial scan coding a response.

**Partial Response (PR):** Decrease of >50% in the product of two diameters with the patient off all steroids, or on adrenal maintenance only; PR will be coded only if confirmed by a second CT/MR scan performed a minimum of 4 weeks after the initial scan.

**Stable Disease (SD):** shall be defined as the circumstance when the scan shows no change. Patients should be receiving stable or decreasing doses of steroids. This will not need a confirmatory scan.

**Progression (P):** shall be defined as a  $> 25\%$  increase in tumor area (*two diameters*) provided that the patient has not had his/her dose of steroids decreased since the last evaluation period. This will not need a confirmatory scan. A concomitant decrease in steroid dose will rule out a progression designation during the first two months after completion of XRT. (Note: Under exceptional circumstances disease progression may be declared in the absence of an increase in tumor size)

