#### 11.1.4.1 Evaluation of Target lesions by MRI using McDonalds criteria

Response	WHO/modified McDonald Criteria
CR (complete response)	Complete disappearance of all enhancing disease and off all steroids
PR (partial response)	<math>\geq 50\%</math> reduction in the sum of products of the perpendicular diameters of up to 2 target lesions* plus no new lesion, no progression of non-measurable CNS lesion, no increasing steroid requirements, and no worsening of neurologic symptoms
SD (stable disease)	$< 50\%$ reduction in size or $< 25\%$ increase in size.
PD † (progressive disease)	
 
• <math>\geq 25\%</math> increase of up to 2 target CNS lesions relative to nadir
 
• New CNS lesions
 
• unequivocal progression (defined below‡)
 
• Tumor-related increase in steroid dose
 
• New or worsening tumor-related neurologic symptoms
 

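### The brain-lesion baseline rule (all lesions of 10 mm or more, sum of diameters) does not match the scoring rules (area or products, up to two lesions), and the visible text does not fix the scored pair

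*Combined protocol and SAP*

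**What the plan says.** Four places define how brain lesions are measured.

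- **Section 11.1.2, Disease Parameters.** Measurable lesions are "brain lesions that can be accurately measured in at least one dimension", with a 10 mm minimum. All of them "should be identified as target lesions and recorded and measured at baseline", with no limit on number. "Target lesions should be selected on the basis of their size", with reproducibility as a second consideration. The only baseline summary is this: "A sum of the diameters for all target lesions will be calculated and reported as the baseline sum diameters".
- **Section 11.1.4, Definition of CNS response.** Partial response is "Decrease of >50% in the product of two diameters". Progression is a rise of more than 25%, expressed as "increase in tumor area". Neither has a lesion limit.
- **Section 11.1.4.1, table.** Partial response is a reduction of at least 50% "in the sum of products of the perpendicular diameters of up to 2 target lesions". Progression is a rise of at least 25% "of up to 2 target CNS lesions relative to nadir", and that row names no measure. New lesions, unequivocal progression, a tumor-related steroid increase and neurologic worsening also count as progression.
- **Section 13.0, Sample size and study duration.** Response is to be assessed by CNS RECIST 1.1.

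Sections 11.1 and 11.1.4 name the WHO/modified McDonald criteria for the brain. Section 11.1.3 asks for the same method at baseline and follow-up. Section 11.1.4 collects the images for ad hoc central review.

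**The concern.** The primary endpoint is the proportion of patients without CNS progression at 3 months, and for many patients that will rest on a percentage change in lesion size. A percentage change needs a defined lesion set, a defined measure and a baseline value on the same scale. Here the baseline paragraph uses one lesion set and scale, the scoring text and table use others, and the statistical section names a third system.

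Two readers following the document in good faith could score the same pair of scans differently. Where there are more than two targets, the choice of lesions could be made with the week-12 scan in view, because no visible rule prevents it. The trial has one arm, central review is only ad hoc, and the treating physician's progression date prevails in a discrepancy (11.1.4, Time to CNS Progression). Success is declared at 8 of 20, so a few reclassified patients could matter.

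**Working it through.** **The plan's own figure.** For 8 of 20, 0.40 ± 1.96 × √(0.40 × 0.60 / 20) = 18.5% to 61.5%, as section 13.0 states. The point below does not depend on this interval.

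**Step 1: the rules side by side.**

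| Place | Lesions | Measure |
|---|---|---|
| 11.1.2 | all of 10 mm or more | sum of diameters |
| 11.1.4 text | no limit | product of two diameters, or area |
| 11.1.4.1, partial response | up to 2 | sum of products |
| 11.1.4.1, progression | up to 2 | not named |
| 13.0 | not stated | CNS RECIST 1.1 |

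**Step 2: the baseline sum cannot be converted.** A lesion with a longest diameter of 22 mm may have a product of 22 × 22 = 484 mm² or 22 × 12 = 264 mm². Summing both diameters does not help: 22 + 12 = 17 + 17 = 34, but the products are 264 and 289 mm². The thresholds differ too. For uniform growth, +25% in area is √1.25 − 1 = 11.8% in each diameter, while +25% in diameter is 1.25² − 1 = 56% in area. The 20% diameter rise used for RECIST in section 11.2.3 is 1.2² − 1 = 44% in area.

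**Step 3: the pair can decide the call.** Take four lesions of assumed size, 22×18, 18×15, 14×12 and 12×10 mm, read at week 12 as 22×18, 18×15, 17×15 and 15×13 mm.

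| Lesions scored | Baseline | Week 12 | Change |
|---|---|---|---|
| two largest | 666 mm² | 666 mm² | 0% |
| two smallest | 288 mm² | 450 mm² | +56.3% |
| other four pairs | – | – | +14.5% to +19.9% |
| all four, area | 954 mm² | 1116 mm² | +17.0% |
| all four, longest diameters | 66 mm | 72 mm | +9.1% |

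Only the two smallest give progression by size.

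**Step 4: outer bounds on lesion choice.** Simulation, all inputs assumed: equal baseline areas; log-area change per lesion = shared normal term + lesion-specific normal term, both with mean 0; progression if the summed area of the scored lesions rises by at least 25%. The range runs from always scoring the two most-shrunk lesions to always scoring the two most-grown. Other progression triggers are ignored.

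| Lesions | SD per lesion / shared | Fixed pair | Range |
|---|---|---|---|
| 5 | 0.5 / 0.3 | 36% | 6% to 70% |
| 3 | 0.5 / 0.3 | 36% | 18% to 52% |
| 3 | 0.2 / 0.5 | 34% | 28% to 40% |
| 1 or 2 | any | – | no choice, no effect |

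Scoring all five lesions in the first row gives 37%, so the issue is the choice of pair rather than the number of lesions.

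**Step 5: reading error with no minimum second diameter.** Assume an unchanged lesion, an independent error of 1 mm SD on each diameter at both scans, and whole-millimetre readings. A rise of at least 25% in the product is then called in about 30% for 10 × 4 mm, 13% for 10 × 10 mm and 1.5% for 20 × 20 mm. If the longest baseline reading must be at least 10 mm, the first two fall to 25% and 9%. With 0.5 mm SD and no such restriction, 10 × 10 mm falls to about 1.4%. One millimetre can be enough: 10 × 5 against 10 × 4 is exactly +25%, which meets the table's threshold (at least 25%) but not the text's (more than 25%).

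**Step 6: what misclassification would do to the success rule.** If a fraction m of true progressors were scored progression-free (assumed, in one direction only), a true 15% rate becomes 0.15 + 0.85m. The chance of 8 or more of 20 is 0.006 at m = 0, 0.026 at 5%, 0.075 at 10% and 0.292 at 20%. The documents give no value for m.

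**The case against.** A reader might infer that baseline areas are not recorded at all. The documents do not support that. Sections 11.1 and 11.1.4 name bidimensional criteria, 11.1.3 asks for the same method at both times, 11.1.2 does not confine measurement to one diameter, and the images are kept, so areas could be measured again. What stands is that the perpendicular diameter and the sum of products are not explicitly required at baseline. Measuring them again after week 12 would be done with the outcome in view.

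A reader might also infer that the pair is left wholly open. That too goes beyond the text. Section 11.1.2 favours large, reproducible lesions, moves to the next largest where needed, prefers non-cystic lesions and excludes lesions treated with radiosurgery. This points to the two largest. The table's asterisk on the two-lesion limit leads to a footnote missing from the copy reviewed, which may name the pair. What stands is that 11.1.2 never reduces its targets to two, and no visible text says when the pair is fixed. Even a helpful footnote would leave the all-lesion sum of diameters at odds with the table.

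A third defence is that RECIST was intended, since section 13.0 names it and a sum of diameters would fit it. The explicit CNS definitions are bidimensional, so this confirms the conflict.

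Finally, the wide simulated range needs several equal lesions, mostly independent change and a reader who always takes the extreme pair. With equal lesions the size rule cannot operate. The other progression triggers apply whichever pair is scored. These limits are fair, and the figures are bounds, not forecasts.

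**Conclusion.** The point holds as a conflict between measurement rules that feed the primary endpoint. The defined baseline sum cannot be the reference for the area criteria. The visible text neither explicitly requires the baseline products nor caps the targets at two and fixes them in time. In patients with more than two targets, lesion choice can change whether size-based CNS progression is called.

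The size is uncertain, because the documents give no lesion counts, growth variability or reading error. Under the assumed worst cases the range runs from 6–70% around a fixed-pair value of 36% down to 28–40% around 34%, with no effect for one or two targets. The documents do not show that readers will choose lesions after seeing the scan, or that the result will be biased in a given direction. The change should be made, but the sample size is not affected.

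**What to change.** Use one criterion in sections 11.1.2, 11.1.4, 11.1.4.1 and 13.0. Since 11.1, 11.1.4 and 11.1.4.1 all name or use WHO/modified McDonald, align the rest to it:

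1. In 11.1.2, before the first dose, name up to two target lesions by the existing size and reproducibility rule. Record both perpendicular diameters of each, and report the sum of products as the baseline value in place of the sum of diameters.
2. Score the same lesions at every later scan and treat all others as non-target.
3. State the measure in the progression row of 11.1.4.1, and give the text and table the same lesion limit and threshold sign.
4. Replace CNS RECIST 1.1 in 13.0 with the chosen criterion.

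A minimum size for the second diameter would reduce the reading error in Step 5, but it is optional.

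The cost is protocol wording, plus case report form fields for the second diameter and the sum of products if they are not already there; the form is not among the documents. The downside is that lesions outside the named pair are followed only as non-target.

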#### 11.1.3 Methods for Evaluation of Measurable Disease

All measurements should be taken and recorded in metric notation using calipers. All baseline evaluations should be performed within 30 days of initiation of 1st cycle of Chemotherapy.

The same method of assessment and the same technique should be used to characterize each identified and reported lesion at baseline and during follow-up.

Conventional CT and MRI This guideline has defined measurability of lesions on CT scan based on the assumption that CT slice thickness is 5 mm or less. If CT scans have slice thickness greater than 5 mm, the minimum size for a measurable lesion should be twice the slice thickness. MRI is also acceptable in certain situations (e.g., for body scans).

Use of MRI remains a complex issue. MRI has excellent contrast, spatial, and temporal resolution; however, there are many image acquisition variables involved in MRI which greatly impact image quality, lesion conspicuity, and measurement. Furthermore, the availability of MRI is variable globally. As with CT, if an MRI is performed, the technical specifications of the scanning sequences used should be optimized for the evaluation of the type and site of disease. Furthermore, as with CT, the modality used at follow-up should be the same as was used at baseline and the lesions should be measured/assessed on the same pulse sequence. It is beyond the scope of the RECIST guidelines to prescribe specific MRI pulse sequence parameters for all scanners, body parts, and diseases. Ideally, the same type of scanner should be used and the image acquisition protocol should be followed as closely as possible to prior scans. Body scans should be performed with breath-holding techniques, if possible.

PET-CT At present, the low dose or attenuation correction CT portion of a combined PET-CT is not always of optimal diagnostic CT quality for use with RECIST measurements. However, if the site can document that the CT performed as part of a PET-CT is of identical diagnostic quality to a diagnostic CT (with IV contrast), then the CT portion of the PET-CT can be used for RECIST measurements and can be used interchangeably with conventional CT in accurately measuring

cancer lesions over time. Note, however, that the PET portion of the CT introduces additional data which may bias an investigator if is not routine or serially performed.

#### 11.1.4 Response Criteria

##### Measurement of Response

Gadolinium-enhanced brain MRI will be checked at baseline, 12 weeks after starting treatment, and every 12 weeks thereafter until progression. The slice thickness of MRI should be less than 5 mm throughout the brain (2 to 3 mm thickness is highly recommended). MR imaging will be collected electronically for ad hoc central review of responses.

Response in the brain also will be measured using dimensional measurements (WHO/modified McDonald's criteria). Systemic responses will be assessed using the revised Response Evaluation Criteria in Solid Tumors (RECIST) guideline (version 1.1) (Eisenhauer 2009).

##### **Time to CNS Progression**

Patients will be followed clinically and radiographically. The date at which the tumor is documented to have first enlarged (brain or systemic progression) by 25% from best response (steroid dose stable or increased, neurologically stable or worse) will be considered the date of tumor progression. Time to progression will be the interval between the date of study entry and the date of tumor progression. In the event of a discrepancy and for the purposes of analysis, the treating physician's date of tumor progression will be deemed to be correct. Tissue confirmation of CNS tumor progression by stereotactic biopsy or other surgical procedure is encouraged to rule out treatment effect as a cause of radiographic worsening. Ancillary imaging techniques such as PET imaging, perfusion MRI, or MR spectroscopy of all "recurrent" or "progressive" lesions of CNS is recommended for patients at centers with access to these technologies.

Responses in the CNS and systemic compartments will be assessed by the same criteria in order to avoid confusion in the conduct of the trial. CNS disease will be imaged by MRI with gadolinium, and systemic disease will be imaged by CT scan with IV contrast.

##### **Definition of CNS response to eribulin mesylate**

Residual enhancing, non-enhancing, or minimally enhancing tumor:

PR or CR should be confirmed at least 4 weeks after scan showing response.

**Complete Response (CR):** shall be defined as the circumstance when the tumor is no longer seen by neuroimaging, with the patient off all steroids, or on adrenal maintenance only; CR will be coded only if confirmed by a second CT/MR scan performed a minimum of 4 weeks after the initial scan coding a response.

**Partial Response (PR):** Decrease of >50% in the product of two diameters with the patient off all steroids, or on adrenal maintenance only; PR will be coded only if confirmed by a second CT/MR scan performed a minimum of 4 weeks after the initial scan.

**Stable Disease (SD):** shall be defined as the circumstance when the scan shows no change. Patients should be receiving stable or decreasing doses of steroids. This will not need a confirmatory scan.

**Progression (P):** shall be defined as a  $> 25\%$  increase in tumor area (*two diameters*) provided that the patient has not had his/her dose of steroids decreased since the last evaluation period. This will not need a confirmatory scan. A concomitant decrease in steroid dose will rule out a progression designation during the first two months after completion of XRT. (Note: Under exceptional circumstances disease progression may be declared in the absence of an increase in tumor size)

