**Stable Disease (SD)"**

Neither sufficient shrinkage to qualify for PR nor sufficient increase to qualify for PD, taking as reference the smallest sum diameters while on study.

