#### **Secondary Objective 2.2.3:** CBR at 12 weeks

We will sum the proportion of the patients with complete response, partial response and stable disease at 12 weeks (CBR). We will then calculate the proportion (and 95% CI) of patients with CBR at 12 weeks.

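### Section 11.1.4 gives two conflicting sets of CNS response categories, and one leaves some patients without progression in no category, so the week-12 clinical benefit rate is not fully defined

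*Combined protocol and SAP*

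**What the plan says.** Two sets of CNS categories stand side by side in Section 11.1.4.

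- **Text definitions** (Definition of CNS response to eribulin mesylate). SD "shall be defined as the circumstance when the scan shows no change", with steroids stable or falling. PR is a fall of more than 50% "in the product of two diameters with the patient off all steroids, or on adrenal maintenance only", and "PR will be coded only if confirmed by a second CT/MR scan performed a minimum of 4 weeks after the initial scan". CR carries the same confirmation and steroid conditions. Progression is growth in area of more than 25%.
- **Table in 11.1.4.1** (WHO/modified McDonald). SD is "< 50\%$ reduction in size or $< 25\%$ increase in size". PR is a reduction of at least 50% "in the sum of products of the perpendicular diameters of up to 2 target lesions". It also requires "no increasing steroid requirements, and no worsening of neurologic symptoms", with no new or progressing CNS lesions. The row states no confirmation. PD begins at 25% growth and also includes new lesions, a tumor-related steroid increase, and neurologic worsening.

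The endpoint that uses these categories is CBR. Section 2.2.3 defines it as CR, PR and SD at 3 months. Section 13.1 says: "We will sum the proportion of the patients with complete response, partial response and stable disease at 12 weeks (CBR". Neither section says how an unconfirmed response is counted, or whether CBR is CNS only.

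Three other places bear on this:

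- The best-overall-response table restricts its confirmation footnote to non-randomized trials whose primary endpoint is response.
- The sample size text in Section 13.0 names a third system, CNS RECIST 1.1.
- Systemic SD in Section 11.2.3 is a residual class: "Neither sufficient shrinkage to qualify for PR nor sufficient increase to qualify for PD".

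**The concern.** CBR is a sum over categories, so it is well defined only if every patient falls into exactly one category. The two sets disagree on SD, on the size cut-off for PR, on confirmation, on steroids, and on the progression cut-off. The text set also leaves gaps between its categories. A patient whose brain disease has shrunk markedly by week 12 could end up outside CR, PR and SD without having progressed.

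What is at stake is the secondary CBR. It could be biased downward, or it could depend on a coding choice made after the scans are seen, in a single-arm trial. The CNS response rate in Section 2.2.1 depends on the same choice between the two PR rules.

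**Working it through.** **1. Classify the week-12 change in tumor area under each set.** Other conditions in each row are taken as met. *None* means no category applies. The text column reads the no-change wording literally.

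| Week-12 change | Text definitions | Table in 11.1.4.1 |
|---|---|---|
| −60%, never confirmed | none | PR |
| −60%, confirmed, off steroids or adrenal maintenance only | PR | PR |
| −60%, confirmed, stable steroid dose above adrenal maintenance | none | PR |
| −50% exactly | none | PR |
| −40%, −10%, +10%, +24% | none | SD |
| 0% | SD | SD |
| +25% exactly | none | PD |
| +30%, steroids not decreased | progression | PD |

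The table's size bands leave no hole. The text definitions leave two.

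- The first concerns shrinkage of more than 50% that fails the confirmation or steroid condition. Borrowing the table's SD band does not close it, because that band stops short of 50% reduction.
- The second concerns every smaller change that is not progression. It opens only if the no-change wording is read literally.

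**2. Is a missing confirmation realistic?** Section 11.1.4 schedules MRI at baseline, week 12 and every 12 weeks after that. No 4-week confirmatory scan appears in the Section 10.2 calendar, so the next scheduled scan is at 12 + 12 = 24 weeks. Calendar note d ties MRI to being on eribulin, and Section 3.4 ends treatment for systemic progression or toxicity, among other reasons. A CNS responder who stops between weeks 12 and 24 has no calendar MRI that could confirm her response. The steroid route is also open, since criterion 4.1.5 admits patients on a stable steroid dose.

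**3. Size.** The plan gives no figure for CBR. Its one interval is in Section 13.0: 8 of 20 gives 40%, 95% CI 18.5–61.5%. The normal approximation reproduces it:

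0.40 ± 1.96 × √(0.40 × 0.60 / 20) = 0.40 ± 0.215, that is 18.5–61.5%.

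With n = 20, each patient dropped from the CBR numerator costs 1/20 = 5 percentage points. As an illustration, assume 8 of 20 have no CNS progression at week 12 and k of them are left uncategorised:

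| k | CBR | 95% CI, plan's method |
|---|---|---|
| 0 | 8/20 = 40% | 18.5–61.5% |
| 1 | 7/20 = 35% | 14.1–55.9% |
| 2 | 6/20 = 30% | 9.9–50.1% |
| 3 | 5/20 = 25% | 6.0–44.0% |
| 4 | 4/20 = 20% | 2.5–37.5% |

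Exact (Clopper-Pearson) limits are 19.1–63.9% for 8/20 and 8.7–49.1% for 5/20. The value of k is an assumption; the documents do not give it.

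**The case against.** The strongest reply is that the table alone settles the matter. Sections 11.1 and 11.1.4 name WHO/modified McDonald as the CNS criteria, and 11.1.4.1 is the table under that name. It makes the patient with 60% shrinkage PR and needs no second scan. On that reading all 8 non-progressors in the illustration count and CBR stays at 40%. This stands as far as it goes: the lower figures arise only when the text rules on confirmation and steroids are applied. But the text definitions are equally explicit, and nothing says that the table overrides them.

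A second reply is that confirmation may not block a week-12 count. The Duration of Response text dates a response from when the measurement criteria are first met, so a response confirmed later could be credited to week 12. The best-overall-response footnote limits confirmation to trials with response as the primary endpoint, and Sections 2.1 and 13.0 make 3-month CNS PFS primary. This narrows the problem to responses never confirmed or failing the steroid condition. It does not remove it, because Section 11.0 calls response in the brain the primary endpoint, so the footnote cannot decide the case.

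A reader might infer that the plan counts such a patient as having no benefit. No section says so; it is what a literal sum would give. A reader might also infer that CBR must equal the primary proportion. That requires CBR to be CNS only, which Sections 2.2.3 and 13.1 do not state.

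**Conclusion.** The two sets of CNS categories contradict each other, and the text set is not exhaustive. Under its coding rules, a patient with more than 50% shrinkage at week 12 that is never confirmed, or who stays on a stable steroid dose above adrenal maintenance, is neither PR nor SD under either SD wording. With the no-change wording read literally, the same holds for any smaller change that is not progression. A literal CR + PR + SD sum can therefore omit patients without CNS progression and bias CBR downward by 5 percentage points each at n = 20. How many would be affected is unknown.

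This is an unreconciled rule, not a demonstrated miscount. Nor does it threaten the primary result. The 8-of-20 rule counts patients without CNS progression, so labelling such a patient PR, SD or nothing does not change it. The progression cut-offs differ only at growth of exactly 25%, and no effect is claimed from that here. CBR is a secondary estimate with no decision rule. The correction should be made because it is cheap and removes a choice that would otherwise fall after the data are seen.

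**What to change.** 1. Reconcile the text definitions, the table in 11.1.4.1, the best-overall-response table and the CNS RECIST 1.1 reference in Section 13.0 into one set of CNS categories. The set should have one cut-off each for PR and PD, one steroid condition, and one statement on whether confirmation is required.
2. Make CNS SD the residual class, meaning neither a coded CR or PR nor PD, as systemic SD already is in Section 11.2.3. This fits the statement in Section 11.1.4 that the CNS and systemic compartments are assessed by the same criteria.
3. State that PD takes precedence, including the table's tumor-related steroid increase and neurologic worsening. Otherwise a patient with shrinkage and such an increase would be both PD and clinical benefit.
4. In Sections 2.2.3 and 13.1, state that for week-12 CBR a CR or PR that is unconfirmed, or not codable under the steroid condition, counts as at least SD unless PD criteria are met. State also whether CBR is CNS only.

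No change to what CBR is meant to measure is needed. The cost is protocol and SAP wording only; these changes need no extra scans or patients and do not alter the primary rule.
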